Palatable Eating Motives: Coping Subscale (PEMS)(Burgess, Turan, Lokken, Morse, & Boggiano, 2014). The PEMS Coping subscale is comprised of 4 Likert-like five-choice frequency response items that probe various motives for "eating tasty food and drinks." The instructions include a list of examples of these kinds of foods and sugary drinks. The list of tasty foods was adopted from the Yale Food Addiction Scale (G earhardt, Corbin, & Brownell, 2009) with slight modifications. The Coping motives subscale measures intentionally using palatable food to cope with negative feelings (e.g., to forget about or help with worry, depression, nervousness, a bad mood, or problems). Item response choices range from almost never /never to almost always/always. The trait form for this subscale has been validated using ecological momentary assessment, and both versions are related equally to BMI and changes in emotional eating correlate with changes in BMI over time (Boggiano, Wenger, Turan, Tatum, Morgan, et al., 2015; Boggiano, Wenger, Turan, Tatum, Sylvester, et al., 2015).

Trait Food Craving Questionnaire, Reduced (FCQ-T-r)(Meule, Hermann, & Kubler, 2014). The Trait Food Craving Questionnaire, reduced, is a 15-item measure of behavioral, cognitive, and physical aspects of cravings for different types of food. Item response choices range from 0 (never or n/a) to 5 (always), and the total score is an average of the 15 items. High scores predict how much people crave and eat densely caloric snacks in daily life, and are associated with self-reported failures in dieting (Meule, Lutz, Vogele, & Kubler, 2012; Richard, Meule, Reichenberger, & Blechert, 2017)

Using Food to Cope: this a 2-item questionnaire asking respondents to indicate how they "usually experience a stressful event." Questions include: "I eat more of my favorite foods to make myself feel better" and I eat more than I usually do." Item response choices range from 1 (*a lot*) to 4 (*not at all*). The responses to the items are reverse coded and summed so that higher scores indicate a greater use of food to cope with stress (Tsenkova, Boylan, & Ryff, 2013).

The Reward Based Eating Drive Scale (RED-13) (Mason, et al., 2017): The RED-13 is a 13-item self-report measure that broadly captures the spectrum of reward-related eating (RRE) and may be a useful tool for identifying individuals at risk for overweight or obesity. The RED-13 is designed to capture three dimensions of the RRE construct: lack of control over eating, lack of satiety, and preoccupation with food. RED-13 was also related to self-reported diagnosis of type 2 diabetes as well as cravings for sweet and savory foods (Mason, et al., 2017). Item response choices range from 0 (*strongly disagree*) to 4 (*strongly agree*).

Loss of Control over Eating Scale (LOCES) (Latner et al., 2014): The LOCES scale is a multidimensional scale designed to assess LOC eating in both clinical and nonclinical populations (Latner et al. 2014). Instructions include to ask participants to indicate how often during the past 28 days they have had the following experiences while eating. Each of the 7 questions has a 5- point scale from 1 (*Never*), 2 (*Rarely*), 3 (*Occasionally*), 4 (*Often*), to 5 (*Always*)

Food Acceptance and Awareness Questionnaire (FAAQ) (Juarascio, Forman, Timko, Butryn, & Goodwin, 2011): The FAAQ was designed to measure the acceptance or ability to regulate eating despite urges and cravings and the desire to control these thoughts. The survey is comprised of 10 items and can be

answered using a 7-point likert rating scale ranging from 1 (*never true*) to 7 (*always true*). Higher scores indicate greater acceptance of motivations to eat (Juarascio et al., 2011).

Food Frequency Questionnaire: (FFQ; modified from the Multi-ethnic Study of Atherosclerosis) (**Bild et al., 2002**), a 16-item self-report measure that assesses how frequently an individual eats foods from the following 16 food categories: processed meats, refined grains, whole grains, fruits, vegetables, white potatoes, fried foods, red meat, high-fat dairy, low-fat dairy, nuts/seeds/peanut butter, fish/seafood (not fried), sodas (non-diet), coffee, sweets, and alcohol. Items for each food group are answered on a Likert scale from 1 (rarely or never) to 9 (two times or more per day) in response to the question: *How often do you eat this type of food?* Individual scores for each food item are calculated as the frequency, ranging from 1 to 9.

Domain: Mindfulness

Mindfulness: This will be measured using the Mindful Attention Awareness Scale (MAAS) (Brown & Ryan, 2003), which assesses the tendency to be mindful day to day (15 items).

Mindwandering probes: We created for this study, a two item measure that assesses present mindwandering and the affective content of this mindwandering (attached).

Domain: Health Behaviors

Sleep Quality: overall sleep quality will be assessed using items from the Pittsburgh Sleep Quality Index (Buysse et al., 1989) to assess sleep onset latency, efficiency, duration, and subjective quality (5 items)

Physical activity: The Stanford Leisure-Time Activity (L-Cat) measures usual physical activity habits. We will use a 1-item measure to assess leisure physical activity (Kiernan et al., 2013) (1 item).

Domain: Physical Health

Self-reported health: This will be measured using the 12-item Short Form Survey (SF-12), which includes items related to mental and physical well-being and is consistently used in health research (12 items)

Stress-related somatic complaints: This measure was created for this study (attached) and asks participants to report on the extent they experience the following symptoms: body/joint pain, headaches, stomachaches, nausea, and cold/flu symptoms (5 items).

Checklist of medical and medication history: participants will complete a short check list on common medical conditions and medications they may or may not endorse.

Domain: Work

Work Engagement: Work engagement will be assessed using the 9 item self-report Utrech Work Engagement Scale (Schaufeli & Bakker 2003) which uses three factors to determine the level of work engagement: vigor, dedication and absorption.

Days of Work Missed: A two item self-report scale will measure the number of days participants have missed work due to either illness or non-illness related reasons.

Burnout: The Bergen Burnout Inventory is a 9-item measure that assesses three components associated with burnout, including exhaustion, cynicism at work, and sense of inadequacy at work (9 items).

Job Strain: The effort-reward imbalance scale will be used to assess job strain. It contains several subscales that measure effort, reward, and overcommitment and is used routinely in both research and occupational settings (Siegrist et al., 2004) (22 items).

Midpoint Questionnaire (week 4):

Mindfulness: This will be measured using the Mindful Attention Awareness Scale (MAAS) (Brown & Ryan, 2003), which assesses the tendency to be mindful day to day (15 items).

Perceived Stress: The Perceived Stress Scale (PSS) is a gold standard measure for stress perceptions, including ratings of feeling overwhelmed, out of control, and stressed, and has been extensively validated (Cohen et al, 1988). (10 items).

Job Strain: The effort-reward imbalance scale will be used to assess job strain. It contains several subscales that measure effort, reward, and overcommitment and is used routinely in both research and occupational settings (Siegrist et al., 2004) (22 items).

Work Engagement: Work engagement will be assessed using the 9 item self-report Utrech Work Engagement Scale (Schaufeli & Bakker 2003) which uses three factors to determine the level of work engagement: vigor, dedication and absorption.

The sub-study participants will also answer the following:

Palatable Eating Motives: Coping Subscale (PEMS) (Burgess, Turan, Lokken, Morse, & Boggiano, 2014). The PEMS Coping subscale is comprised of 4 Likert-like five-choice frequency response items that probe various motives for "eating tasty food and drinks." The instructions include a list of examples of these kinds of foods and sugary drinks. The list of tasty foods was adopted from the Yale Food Addiction Scale (Gearhardt, Corbin, & Brownell, 2009) with slight modifications. The Coping motives subscale measures intentionally using palatable food to cope with negative feelings (e.g., to forget about or help with worry, depression, nervousness, a bad mood, or problems). Item response choices range from almost never /never to almost always/always. The trait form for this subscale has been validated using ecological momentary assessment, and both versions are related equally to BMI and changes in emotional eating correlate with changes in BMI over time (Boggiano, Wenger, Turan, Tatum, Morgan, et al., 2015; Boggiano, Wenger, Turan, Tatum, Sylvester, et al., 2015).

Post intervention Questionnaire (week 8):

Participants will complete all the same questionnaire included in the baseline packet, with the exception of the medical and medication checklist and Adverse Childhood Events questionnaire. They will be asked about the frequency of their sitting meditation practice in the past 8 weeks.

Follow-up Questionnaire (2-months post intervention):

Mindfulness: This will be measured using the Mindful Attention Awareness Scale (MAAS) (Brown & Ryan, 2003), which assesses the tendency to be mindful day to day (15 items).

Perceived Stress: The Perceived Stress Scale (PSS) is a gold standard measure for stress perceptions, including ratings of feeling overwhelmed, out of control, and stressed, and has been extensively validated (Cohen et al, 1988). (10 items).

Job Strain: The effort-reward imbalance scale will be used to assess job strain. It contains several subscales that measure effort, reward, and overcommitment and is used routinely in both research and occupational settings (Siegrist et al., 2004) (22 items).

Work Engagement: Work engagement will be assessed using the 9 item self-report Utrech Work Engagement Scale (Schaufeli & Bakker 2003) which uses three factors to determine the level of work engagement: vigor, dedication and absorption.

The sub-study participants will also answer the following:

Palatable Eating Motives: Coping Subscale (PEMS) (Burgess, Turan, Lokken, Morse, & Boggiano, 2014). The PEMS Coping subscale is comprised of 4 Likert-like five-choice frequency response items that probe various motives for "eating tasty food and drinks." The instructions include a list of examples of these kinds of foods and sugary drinks. The list of tasty foods was adopted from the Yale Food Addiction Scale (Gearhardt, Corbin, & Brownell, 2009) with slight modifications. The Coping motives subscale measures intentionally using palatable food to cope with negative feelings (e.g., to forget about or help with worry, depression, nervousness, a bad mood, or problems). Item response choices range from almost never /never to almost always/always. The trait form for this subscale has been validated using ecological momentary assessment, and both versions are related equally to BMI and changes in emotional eating correlate with changes in BMI over time (Boggiano, Wenger, Turan, Tatum, Morgan, et al., 2015; Boggiano, Wenger, Turan, Tatum, Sylvester, et al., 2015).

Follow-up Questionniare (10-months post intervention; digital meditation condition only):

Mindfulness: This will be measured using the Mindful Attention Awareness Scale (MAAS) (Brown & Ryan, 2003), which assesses the tendency to be mindful day to day (15 items).

Perceived Stress: The Perceived Stress Scale (PSS) is a gold standard measure for stress perceptions, including ratings of feeling overwhelmed, out of control, and stressed, and has been extensively validated (Cohen et al, 1988). (10 items).

Job Strain: The effort-reward imbalance scale will be used to assess job strain. It contains several subscales that measure effort, reward, and overcommitment and is used routinely in both research and occupational settings (Siegrist et al., 2004) (22 items).

Work Engagement: Work engagement will be assessed using the 9 item self-report Utrech Work Engagement Scale (Schaufeli & Bakker 2003) which uses three factors to determine the level of work engagement: vigor, dedication and absorption.

Participants may also complete the following:

U.S. Household Food Security Module: The six-item short form of the survey module and the associated Six-Item Food Security Scale were developed by researchers at the National Center for Health Statistics in collaboration with Abt Associates Inc. and documented in "The effectiveness of a short form of the

household food security scale," by S.J. Blumberg, K. Bialostosky, W.L. Hamilton, and R.R. Briefel (published by the *American Journal of Public Health*, vol. 89, pp. 1231-34, 1999). ERS conducted additional assessment of classification sensitivity, specificity, and bias relative to the 18-item scale.

The sub-study participants will also answer the following:

Palatable Eating Motives: Coping Subscale (PEMS) (Burgess, Turan, Lokken, Morse, & Boggiano, 2014). The PEMS Coping subscale is comprised of 4 Likert-like five-choice frequency response items that probe various motives for "eating tasty food and drinks." The instructions include a list of examples of these kinds of foods and sugary drinks. The list of tasty foods was adopted from the Yale Food Addiction Scale (Gearhardt, Corbin, & Brownell, 2009) with slight modifications. The Coping motives subscale measures intentionally using palatable food to cope with negative feelings (e.g., to forget about or help with worry, depression, nervousness, a bad mood, or problems). Item response choices range from almost never /never to almost always/always. The trait form for this subscale has been validated using ecological momentary assessment, and both versions are related equally to BMI and changes in emotional eating correlate with changes in BMI over time (Boggiano, Wenger, Turan, Tatum, Morgan, et al., 2015; Boggiano, Wenger, Turan, Tatum, Sylvester, et al., 2015).

Attach any unpublished instruments in the 'Other Study Documents' section of the Initial Review Submission Packet form after completing the study application. Published instruments should NOT be attached.

7.12 * BIOSPECIMEN COLLECTION: Are you drawing any blood or collecting other biosamples (e.g. tissue, buccal swabs, urine, saliva, hair, etc.) for analysis under this protocol and/or storage for future research: (REQUIRED)

O Yes O No

7.13 STATISTICAL METHODS: Briefly summarize the methods and types of analyses that will be performed:

We will employ chi-square and *t*-tests to examine group difference in baseline in demographics and measures obtained by our baseline questionnaire. Intervention effects on each outcome were tested using linear mixed models with Time (t1 and t2) was included as a within-person factor and intervention group as a between-person factor. We will analyze the data using an intent-to-treat framework, and carry forward latest data point in our final analysis. Alpha's were set at .05 for each outcome. We used eta-squared as our effect size index.

To investigate dose response effects, we will examine whether number of medication sessions moderates the interventon effects among those in the digital meditation group. In this regard, we will test a 2-way interaction (number of weekly meditation*time). All analyses will be conducted in SPSS Version 24 and STATA 13.1.

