 Other UC Campus Other institution Other community-based site Foreign Country Sovereign Native American nation (e.g. Navajo Nation, Oglala Sioux Tribe, Havasupai, etc.) 6.14 * RELYING ON AN EXTERNAL IRB: (REQUIRED) Does this application include a request to rely external IRB (a central IRB (other than the NCI CIRB) or an external IRB (other UC campus, commercial, or institutional): ○ Yes No 7.0 Research Plan and Procedures 	on an
 Other UC Campus Other institution Other community-based site Foreign Country Sovereign Native American nation (e.g. Navajo Nation, Oglala Sioux Tribe, Havasupai, etc.) 6.14 * RELYING ON AN EXTERNAL IRB: (REQUIRED) Does this application include a request to rely external IRB (a central IRB (other than the NCI CIRB) or an external IRB (other UC campus, commercial, or institutional): ○ Yes No 7.0 Research Plan and Procedures 7.1 HYPOTHESIS: Describe the hypothesis or what the study hopes to prove: 	on an

Hypothesis 2: Participants randomized to the 8-week digital meditation intervention will report greater increases in subjective mindfulness, as measured by the Mindful Awareness and Attention Scale, compared to those in the waitlist control condition. The increase in mindfulness will statistically mediate improvements in global stress perception and job strain.

Hypothesis 3: Treatment adherence to the 8-week digital meditation intervention will moderate observed treatment effects, such that improvements in global stress perception and job strain will be stronger among participants who completed more meditations.

Sub-study:

Hypothesis 1. Compared to the Waitlist control condition, participants randomized Digital Meditation, Healthy Eating, or Digital Mediation+Healthy Eating will show greater decreases in blood pressure, improvements in metabolic outcomes, and improvements in measures of psychological stress. Effects will be strongest in the Digital Meditation+Healthy Eating condition.

7.2 AIMS: List the specific aims:

Aim 1: To test the effects of a digital meditation intervention, compared to a waitlist control condition, on global perceptions of stress and job strain in a sample of UCSF employees.

Aim 2: To identify whether increases in mindfulness serves as a pathway through which digital meditation affects reports of stress and test whether treatment adherence moderates treatment-related stress effects.

Sub-study

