We recently investigated whether a mindfulness meditation program delivered via a smartphone application (app; Headspace) could improve psychological well-being, reduce job strain, and reduce ambulatory blood pressure during the workday. Participants were 238 healthy employees from two large UK companies that were randomized to a wait-list group or a mindfulness meditation practice app. Use of the app was associated with significant improvement in well-being, job strain, and perceptions of workplace social support relative to the wait-list control group. Meditating a greater number of times (i.e., better treatment adherence) was associated with the greatest improvements in psychological outcomes. Participants who completed 25 or more meditation sessions over 8 weeks also had significantly lower self-measured systolic blood pressure over the course of one day compared to the control condition participants at the follow-up time point. Sustained positive effects of the intervention were seen for well-being and job strain 8 weeks after the end of the intervention period. This trial suggests that almost daily brief mindfulness meditations delivered via smartphone can improve outcomes related to workplace stress and well-being, with potentially lasting effects.

This study is presently under revision in a peer-reviewed journal:

Bostock, S., [name], [name], Steptoe, A. Mindfulness on-the-go: Effects of a mindfulnessmeditation app on work-related stress. *Under revision at Journal of Occupational Health Psychology*

7.6	* TREATMENT PROTOCOL: Is this a treatment study, i.e. does this study intend to provide treatment
	to individuals with a medical or psychological condition: (REQUIRED)

⊙ Yes ○ No

7.7 * BILLABLE PROCEDURES: Does this study involve any procedures, lab tests or imaging studies that have a CPT code and could be billable to patients, their insurance, Medi-Cal, Medicare, or any other entity (answer 'Yes' even if the study is going to pay for all the procedures): (REQUIRED)

O Yes O No

If you are not sure if your study involves billable procedures, send an email to the UCSF Office of Clinical Research (OCR) for help answering this question.

7.8 * COMMON RESEARCH ACTIVITIES: Types of research activities that will be carried out. Check all that apply and describe in more detail in the 'Procedures / Methods' section: (REQUIRED)

✓ Interviews, questionnaires, surveys	
Educational or cognitive tests	
Focus groups	

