Daily Diary (sub-study only): During the week prior to randomization and week 7 of the intervention period, particiants are asked to complete a nightly diary and morning diary for 7 consecutive days. These diaries ask questions related to daily behaviors, sleep, mood and other related topics (see attached file). Randomization (main-study)

Upon completing the baseline questionnaire, participants enrolled in the main study will be randomomized to the following conditions:

Digital Meditation Condition (Headspace): The intervention period will last for a total of 8-weeks (56 ± 2 days). Subjects in the Headspace group will be given simple instruction on how they should begin the journey (i.e. begin with Basics 1 followed by the Stress Pack, one 10 minute session per day). Subjects in the waitlist control group will not be given access to Headspace and will be instructed to refrain from any mindfulness or meditation. Active daily usage data in the Headspace group will be captured anonymously via the Headspace app and provided to UCSF as a part of the final analysis. App usage (engagement) will be tracked weekly for each participant.

Waitlist Condition: Participants in this condition will not receive any further study contact during the study window, with the exception of email links to questionnaire batteries at week 4 (midpoint assessment), week 8 (post-intervention), and 4-month follow-up. Once the 4-month follow up is completed or that time has lapsed, the study participant will be provided access to Headspace for the same duration (12 months) as is the case for those randomized to the digital meditation group.

Randomization (sub-study):

Upon completing the baseline questionnaire battery and 7 days of morning and nightly diaries and Fitbit measurement, participants will be randomized to one of the following study conditions:

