Re-engagement protocol: As with any digital intervention study, attrition is common. In an effort to minimize attrition in this study, we have developed a re-engagement protocol. We will send an engagement text message to each participant starting about one week into their participation and for each subsequent week, for 7 weeks. The text message content for the intervention group will consist of gentle reminders to continue to meditate, along with tips to stay active and engaged in the study. For the waitlist control group, these weekly messages will consist of encouragements and brief reminders of participation requirements (see attached doc for specific text). If a participant does not engage after about 2 weeks, then he/she will receive a phone call from our research staff. For those participants who do not answer the phone, the study staff will leave a voicemail and a subsequent text message asking to call them back, and follow up again the next day with another text message. They only hear back from the staff in 2 weeks if they continue to refrain from the meditation app.

Sub-study: Participants will follow the same re-engagement protocol listed above, with minor modifications for the healthy eating groups.

Those in the healthy eating groups will participate in 3 separate booster phone calls (5-10 minutes) to check-in regarding progress and barriers towards healthy eating goals, and feasibility/acceptability of the brief eating intervention. Participants will receive automated text message pings approximately 3 times per week. The pings will provide reminders about mindful eating (including a link to audio sessions on cravings and mindful eating). The pings will occur during identified times of "high vulnerability" from the initial counseling session.

7.10 STANDARD CLINICAL PRACTICE: To what extent, if any, do the planned research procedures differ from the care that people would otherwise receive at this institution or the study site if not being done locally:

The standard care that participants receive will not change.

7.11 INSTRUMENTS: List all questionnaires, surveys, interview, or focus group guides that will be used for this study:

If the instruments are not complete or not available because they will be developed as part of this study, describe the basic content or include an outline and submit the final versions to the IRB with a modification for approval prior to use.

Eligibility Screening.

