9.0 Sample Size and Eligibility Criteria	
9.1 ENROLLMENT TARGET: How many people will you enroll:	
10000	
If there are multiple participant groups, indicate how many people will be in each group:	
We will screen a high number of potential participants to carry out this study. In this regard, we will screen as many as 10000 individuals and thus as many as 10000 individuals will complete a consent form to be screened. Of those who complete the screening, we anticipate that we will consent into the study 2000 participants. We will randomize 1000 participants to our digital mediation condition (Headspace) and 1000 to the waitlist control condition.	
9.3 SAMPLE SIZE JUSTIFICATION: Explain how and why the number of people was chosen. For mul studies, this is referring to the number that will be enrolled across all sites:	lti-site
We are interested in testing a digital intervention with limited contact by study investigators (i.e., no in person contact). As such, participant attrition is to be expected. Our prior study (Bostock et al., under revision) detected effects in a sample of < 250 participants. We expect that our sample size will be well powered to detect improvements in our self-report measures in response to our treatment intervention.	
9.4 * PARTICIPANT AGE RANGE: Eligible age ranges: (REQUIRED)	
 □ 0-6 years □ 7-12 years □ 13-17 years ☑ 18-64 years ☑ 65+ 	
9.5 * STUDY POPULATIONS: Data will be collected from or about the following types of people (che that apply): (REQUIRED)	eck all
☐ Inpatients ☐ Outpatients	
Family members or caregivers Providers	
People who have a condition but who are not being seen as patients Healthy volunteers	
☐ Students ☑ Staff of UCSF or affiliated institutions	
☐ None of the above	
9.6 * SPECIAL SUBJECT GROUPS: Check the populations that may be enrolled: (REQUIRED)	
 □ Children / Minors □ Adult subjects unable to consent for themselves □ Adult subjects unable to consent for themselves (emergency setting) 	
Subjects with diminished capacity to consent Subjects unable to read, speak or understand English	
☐ Pregnant women ☐ Fetuses	
☐ Neonates ☐ Prisoners	
Economically or educationally disadvantaged persons	

V	None of the above	
	INCLUSION CRITERIA: Briefly describe the population(s) that will be involved in this study. Incampone that data will be collected from or about (e.g. patients, healthy controls, caregivers, proadministrators, students, parents, family members, etc.):	

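### Section 7.13 carries the latest value forward although attrition is expected, with no missing-data assumption or sensitivity analysis; if loss differs by arm and scores drift, the primary contrasts err in either direction

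*Combined protocol and SAP*

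**What the plan says.** Section 7.13 describes the main-study model as "linear mixed models with Time (t1 and t2) was included as a within-person factor and intervention group as a between-person factor", without tying t1 and t2 to visits. It then gives the only missing-data rule for the main study: "We will analyze the data using an intent-to-treat framework, and carry forward latest data point in our final analysis". The Statistical Analysis Plan at the end of the document is a week-8 ANCOVA of the four sub-study arms. It does not mention missing data, so it neither replaces nor supplements that rule.

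Loss is foreseen but not quantified. Section 9.3, noting the lack of in-person contact, says: "As such, participant attrition is to be expected". Section 7.9 says: "In an effort to minimize attrition in this study, we have developed a re-engagement protocol".

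On contact by arm, section 7.9 is not consistent. The re-engagement text sends weekly messages to every participant and describes separate content for the waitlist. The waitlist paragraph says: "Participants in this condition will not receive any further study contact during the study window, with the exception of email links to questionnaire batteries". The repeat staff contact is worded around app use: "They only hear back from the staff in 2 weeks if they continue to refrain from the meditation app".

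**The concern.** Perceived stress (PSS) and job strain are the primary outcomes. Carry-forward assumes that a leaver's score stays where it was last seen, and the plan neither states nor defends this. Any change that would have happened in both arms anyway is then credited in proportion to how many people stayed in each arm. If the proportions differ, part of that shared change appears as a treatment difference. The trial could understate a benefit, or report one that does not exist.

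A shared fall in PSS is plausible because entry requires a score of 15 or higher. PSS is measured again at baseline, however, so part of that fall may come before the trial's starting value. Job strain has no entry threshold, so its drift cannot be presumed.

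**Working it through.** The plan gives no figure to reproduce: no loss rate, SD, correlation, drift or effect. Everything below is an illustration with assumed inputs.

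**Inputs.** From the documents: 500 per arm (1,000 in total, section 4.1, taking equal allocation) or 1,000 per arm (section 9.1); alpha 0.05, taken as two-sided; visits at baseline, week 4 and week 8. Assumed: SD 6; correlation 0.6 between visits; effect δ = 1.5 PSS points in those who stay; shared fall m = 2 points (m = −2 for a rise); loss dT (app) and dC (waitlist), random within arm; half of losses before week 4; f = 0.6 of the change reached by week 4.

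**Formula.** The share of full change credited in an arm is k = 1 − d(1 − f/2) = 1 − 0.7d. The expected carried-forward contrast is kT·δ + m(kT − kC).

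The true effect of assignment depends on what app-arm leavers keep: δ if the full benefit, kT·δ if only what they had reached, (1 − dT)·δ if none. The second term of the contrast is an error under all three.

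| Loss app/waitlist, drift | Truth: full / as reached / none | Carry-forward | Maximum likelihood | Control-based |
|---|---|---|---|---|
| 30%/30% | 1.50 / 1.185 / 1.05 | 0.79×1.5 = 1.185 | 1.50 | 1.05 |
| 40%/20%, fall of 2 | 1.50 / 1.08 / 0.90 | 0.72×1.5 − 0.14×2 = 0.80 | 1.50 | 0.90 |
| 20%/40%, fall of 2 | 1.50 / 1.29 / 1.20 | 0.86×1.5 + 0.14×2 = 1.57 | 1.50 | 1.20 |
| 40%/20%, rise of 2 | 1.50 / 1.08 / 0.90 | 1.08 + 0.28 = 1.36 | 1.50 | 0.90 |
| 20%/40%, rise of 2 | 1.50 / 1.29 / 1.20 | 1.29 − 0.28 = 1.01 | 1.50 | 1.20 |

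At equal loss, carry-forward is 21% too small if leavers would have had the full benefit, correct if they keep what they had reached, and 13% too large if they lose it all. With unequal loss it can land below all three truths (0.80, 1.01) or above all three (1.57).

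**Type I error (δ = 0).** The false shift is m × 0.7 × the gap in loss. Change-score variance is 2×36×(1 − 0.6) = 28.8 for an observed or week-4 change and 0 for a carried baseline. At 40%/20%, adding the spread from unequal credited drift, the arm variances are 0.8×28.8 + 0.61 = 23.65 and 0.9×28.8 + 0.39 = 26.31. The SE is then √(49.96/500) = 0.316, or 0.224 at 1,000 per arm.

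| Loss | False shift | Rejection, 500 per arm | Rejection, 1,000 per arm |
|---|---|---|---|
| Equal, or no drift | 0 | 5% | 5% |
| 25%/20% | 0.07 | 5.5% | 6.1% |
| 30%/20% | 0.14 | 7.2% | 9.5% |
| 40%/20% | 0.28 | 14.4% | 24.0% |

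Simulation (2,000 replicates per cell) gave 13–16% and 22–23% for the 20-point gap. Maximum likelihood held null rejection at 4.4–6.0% in one run and 3.1–6.0% in another. The 3.1% is lower than Monte Carlo error readily explains, so I rely on the former.

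**Which value is carried.** Because only t1 and t2 are named, baseline might be carried even when week 4 exists. With a 2-point drift and baseline carried for every leaver, the 20-point gap gives about 28% (500 per arm) and 48% (1,000); with a 1-point drift it gives 10–12% and 15–17%.

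**Not simulated:** loss linked to the score itself, and the 4-month visit.

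**The case against.** Four objections have force.

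First, the documents do not show that loss will differ. A reader might infer from the waitlist paragraph that controls are left without retention contact. The re-engagement text contradicts that by sending them weekly messages about participation. Only the follow-up calls are worded around app use. That is too little to predict a 20-point gap.

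Second, maximum likelihood is not always closer to the truth. The documents make full benefit in leavers doubtful: Hypothesis 3 expects effects "such that improvements in global stress perception and job strain will be stronger among participants who completed more meditations", and the preliminary study reports "Meditating a greater number of times (i.e., better treatment adherence) was associated with the greatest improvements in psychological outcomes". These statements concern meditation counts, which are tracked in the app, and not survey non-response, so they do not settle what non-responders gained. But if leavers keep only what they had reached, or lose it, carry-forward is nearer the truth in 7 of the 10 combinations above, and likelihood overstates the effect in all 10. This stands. It is why the likelihood estimate must not be reported alone. It does not rescue carry-forward, whose drift error remains whatever leavers keep.

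Third, a reader might take the table as evidence that the likelihood and control-based estimates bracket the truth. They do so by construction when loss is random within arm: one targets δ, the other (1 − dT)·δ. This says nothing about outcome-related loss.

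Fourth, section 7.13 asks only for a brief summary. Even so, it commits to a specific rule, and no other section supplies another.

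**Conclusion.** The concern holds in conditional form. A stated rule governs both primary outcomes, loss is expected, and no assumption or sensitivity analysis accompanies it. Bias in either direction and inflated type I error follow if loss differs by arm and scores drift in both. In the illustration the inflation runs from about 6% at a 5-point gap in loss to 14–24% at 20 points. With equal loss or no drift, and loss unrelated to outcome, type I error stays at 5%, and the estimate is too small only if leavers would have gone on to gain more than they had reached.

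Two stronger readings are not supported: that the trial will report a false benefit, and that carry-forward reliably shrinks the effect. Both need loss rates and drift that the documents do not give. Confidence is high on the omission and the mechanism; the size of the error cannot be fixed from the documents. This should be corrected before analysis.

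**What to change.** In protocol section 7.13:

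- Delete the carry-forward clause.
- State that the target is the effect of assignment regardless of app use.
- Fit the planned mixed model by maximum likelihood to all observed PSS and job-strain values (baseline, week 4, week 8, 4 months), with week 8 as the primary contrast, under a stated missing-at-random assumption.
- Report loss by arm at each visit.
- Pre-specify a control-based or delta-adjusted sensitivity analysis in which app-arm leavers lose some or all benefit, and report it beside the primary estimate with equal prominence.

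In section 7.9, reconcile the waitlist paragraph with the re-engagement text on what contact the waitlist receives.

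The cost is wording and a few lines of code. These measures are already collected at all four visits, so no new data or participants are needed. The downside is that the missing-at-random estimate overstates the app effect if leavers lose benefit or stop gaining: in the illustration by 16% (1.50 against 1.29) to 67% (1.50 against 0.90). The sensitivity analysis is there to show this.
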